**11.4 Expedited Adverse Event Reporting to DAIDS****11.4.1 Adverse Event Reporting to DAIDS**

The Serious Adverse Event (SAE) Reporting Category will be used for this study. Requirements, definitions, and methods for SAE and expedited reporting of Adverse Events (AEs) are outlined in Version 2.0 of DAIDS EAE Manual, which is available on the RSC website at <http://rsc.tech-res.com/safetyandpharmacovigilance/>.

The DAIDS Adverse Events Reporting System (DAERS) internet-based reporting system must be used for expedited AE reporting to DAIDS. In the event of system outages or technical difficulties, expedited AEs may be submitted via the DAIDS EAE Form. For questions about DAERS, please

contact DAIDS-ES at [[contact]](mailto:[contact]). Site queries may also be sent from within the DAERS application itself.

Sites where DAERS has not been implemented will submit expedited AEs by documenting the information on the current DAIDS EAE Form. This form is available on the RSC website: <http://rsc.tech-res.com/safetyandpharmacovigilance/>. For questions about EAE reporting, please contact the RSC ([[contact]](mailto:[contact])).

#### 11.4.2 Reporting Requirements for this Study

- The SAE Reporting Category, as defined in Version 2.0 of the DAIDS EAE Manual, will be used for this study.
- The study agents for which expedited reporting is required are: LPV/r, RTV, RBT, and RAL.
- As per the SAE and EAE Reporting Categories identified above, any of the following SAEs require expedited reporting regardless of relatedness or association with the study agents listed:
  - Results in death
  - Life-threatening
  - Requires inpatient hospitalization or prolongation of existing hospitalization
  - Results in persistent or significant disability/incapacity
  - Congenital anomaly/birth defects/fetal losses
  - Other important medical events (may not be immediately life-threatening or result in death or hospitalization but may jeopardize the participant or may require intervention to prevent one of the events listed above).
- In addition to the SAEs listed above, additional events required to be reported in an expedited manner for this protocol include the following:
  - Cancers with no other event, regardless of the association
  - All overdoses of study medications
  - IRIS events that are grade 3 or 4
  - All abnormal outcomes of pregnancies occurring at  $\geq$  20 weeks gestation.

#### 11.4.3 Grading Severity of Events

The most current Division of AIDS Table for Grading the Severity of Adult and Pediatric Adverse Events (DAIDS AE Grading Table) is used and is available on the RSC website at <http://rsc.tech-res.com/safetyandpharmacovigilance/>.

#### 11.4.4 Expedited AE Reporting Period

- The expedited AE reporting period for this study is as per the EAE manual.
- After the protocol-defined AE reporting period, unless otherwise noted, only suspected, unexpected serious adverse reactions (SUSARs), as defined in Version 2.0 of the EAE Manual, will be reported to DAIDS if the study staff become aware of the events on a passive basis (from publicly available information).

### 12.0 HUMAN PARTICIPANTS

#### 12.1 Institutional Review Board (IRB) Review and Informed Consent

This protocol and the informed consent documents (Appendix I and Appendix II) and any subsequent modifications will be reviewed and approved by the IRB or ethics committee responsible for oversight of the study. A signed consent form will be obtained from the participant (or parent, legal guardian, or person with power of attorney for participants who cannot consent for themselves, such as those below the legal age of consent). The consent form will describe the purpose of the study, the procedures to be followed, and the risks and benefits of participation. A copy of the consent form will be given to the participant, parent, or legal guardian, and this fact will be documented in the participant's record.

#### 12.2 Participant Confidentiality

All laboratory specimens, evaluation forms, reports, and other records that leave the site will be identified by coded number only to maintain participant confidentiality. All records will be kept locked. All computer entry and networking programs will be done with coded numbers only. Clinical information will not be released without written permission of the participant, except as necessary for monitoring by ACTG, IRB/EC, the US FDA, the NIAID, the OHRP, the local governmental authorities, or the pharmaceutical supporter(s) or designee.

#### 12.3 Study Discontinuation

The study may be discontinued at any time by the ACTG, IRB/EC, the NIAID, the pharmaceutical supporter(s), the US FDA, the OHRP, or other government agencies as part of their duties to ensure that research participants are protected.

### 13.0 PUBLICATION OF RESEARCH FINDINGS

Publication of the results of this trial will be governed by ACTG policies. Any presentation, abstract, or manuscript will be made available for review by the pharmaceutical supporter(s) prior to submission.

#### 14.0 BIOHAZARD CONTAINMENT

As the transmission of HIV and other blood-borne pathogens can occur through contact with contaminated needles, blood, and blood products, appropriate blood and secretion precautions will be employed by all personnel in the drawing of blood and shipping and handling of all specimens for this study, as currently recommended by the Centers for Disease Control and Prevention and the National Institutes of Health.

All dangerous goods materials, including diagnostic specimens and infectious substances, must be transported using packaging mandated by CFR 42 Part 72. Please refer to instructions detailed in the International Air Transport Association (IATA) Dangerous Goods Regulations.

## 1 Introduction

### 1.1 Purpose

This statistical analysis plan has been developed to (1) facilitate discussion of the key statistical analysis components amongst the study team; and (2) provide agreement between the study team and statisticians regarding the statistical analyses to be performed.

The plan contains details of all statistical analyses that will be completed prior to the preparation of the PK and Safety Interim Analysis report.

### 1.2 Closed Team Roster

The PK and Safety Interim Analysis report will be distributed to the team members who attend the SMC Review. This may include, but may not be limited to, the following team members: Protocol Co-Chairs, Protocol Vice-Chair, Protocol Pharmacologist, DAIDS Clinical Representative, Statisticians, and Clinical Trials Specialist.

### 1.3 Protocol Overview

A5290 is a prospective, randomized, open-label, phase 2b study comparing three lopinavir/ritonavir (LPV/r)-based antiretroviral (ARV) regimens among participants in high tuberculosis (TB) endemic resource-constrained settings undergoing treatment for TB and HIV and requiring protease inhibitor (PI)-based antiretroviral therapy (ART). A two accrual period design is being used, including a full pharmacokinetic (PK) and safety evaluation to be conducted when 54-60 participants enrolled during accrual period 1 have completed 28 days of ARV treatment and day  $12 \pm 2$  (after initiation of study-provided ART and TB medications) drug levels are available. An early assessment by the team will also be completed when 10-12 participants per arm have completed 28 days of ARV treatment and day  $12 \pm 2$  drug levels are available.

The study population is HIV-infected persons (male or female) at least 18 years of age with documented HIV infection, a clinical diagnosis of probable or confirmed active TB (including extrapulmonary TB) with susceptibility to rifampin (RIF), and who require a PI-based ARV regimen.

471 participants will be randomized in a 1:1:1 ratio to receive either:

- Arm A  
ART: LPV 400 mg/RTV 100 mg twice daily (BID) + two NRTIs.  
Anti-TB therapy: Isoniazid (INH), rifabutin (RBT), ethambutol (EMB), pyrazinamide (PZA), and pyridoxine.  
After completion of TB treatment through week 72: LPV 400mg/RTV 100mg BID + two NRTIs.
- Arm B  
ART: LPV 800 mg/RTV 200 mg BID + two NRTIs.  
Anti-TB therapy: INH, rifampin (RIF), EMB, PZA, and pyridoxine.  
After completion of TB treatment through week 72: LPV 400mg/RTV 100mg BID + two NRTIs.

- Arm C  
ART: LPV 400 mg/RTV 100 mg BID + two NRTIs + raltegravir (RAL) 400 mg BID.  
Anti-TB therapy: INH, RBT, EMB, PZA, and pyridoxine.  
After completion of TB treatment through week 72: LPV 400mg/RTV 100mg BID + two NRTIs + RAL.

Accrual will place in two accrual periods. Accrual period 1 will enroll 60 participants (20/arm) who will undergo an initial dose-finding period before continuing regular study follow-up. Accrual will then be suspended until the last SMC review of the interim PK and safety evaluation has been completed. Accrual period 2 will open and randomize the remaining participants to either three arms (n=411) or to the remaining two arms (n=TBD) and will be monitored by the DSMB.

Each participant will be followed until week 72.

The primary hypothesis is that, for HIV-1-infected participants with active tuberculosis (TB) who require protease inhibitor (PI)-based antiretroviral therapy (ART), a standard dose LPV/r regimen, with or without RAL, coupled with RBT-based TB treatment is superior to a double dose LPV/r regimen coupled with RIF-based TB treatment.

#### **1.4 Study Monitoring History**

Besides summarizing the monitoring history of A5290, a brief summary of the Early Assessment will be prepared specifically for this report. The Early Assessment occurred when 10-12/arm accrual period 1 participants completed 28 days of ART and day 12 ± 2 (after initiation of study-provided ART and TB medications) PK results were available. The report was sent to the SMC with the TDM's team decision on 14 January 2016.

#### **1.5 PK and Safety Interim Objectives**

##### **1.5.1 PK Criteria**

- 1) For LPV in Arm B, the primary PK parameter is the day 12 ± 2 (after initiation of study-provided ART and TB medications)  $C_{min}$  ( $C_{12}$ ), and the acceptable lower limit value is  $\geq 1$  mg/L. LPV concentrations in Arm B will be judged acceptable if no more than three participants have a  $C_{min} < 1$  mg/L.
- 2) For RBT (Arms A and C), equivalence analyses will compare day 12 ± 2 (after initiation of study-provided ART and TB medications) RBT 24-hour AUC and  $C_{max}$  with control data derived from prior PK studies, as determined by whether the 90% confidence intervals of the ratios of the RBT concentrations (when co-administered with LPV/r) relative to daily RBT concentrations in the absence of LPV/r are fully contained within the pre-specified NEB of 67%-150%. RBT concentrations in Arms A and C will be judged acceptable if equivalence is declared according to these PK parameters.

### **1.5.2 Safety Criteria**

- 1) No more than three participants in any treatment arm experience a Grade 3 or Grade 4 AE “related to study-provided drug(s)” (as deemed by the TDM Team: DAIDS Clinical Representative, Protocol Co-Chairs, Protocol Vice Chair, Protocol Pharmacologist, Statisticians, Data Manager, Laboratory Data Manager, and Clinical Trials Specialist) by 28 days after initiation of study-provided ART and TB medications.
- 2) No more than three participants in any treatment arm discontinue study-provided drug(s) for treatment-limiting toxicity or intolerance (such that PK assessments within the day  $12 \pm 2$  [after initiation of study-provided ART and TB medications] window cannot be completed).

### **1.6 PK Study Objectives**

Since Accrual Period 2 will not open to enroll participants, the PK objectives outlined in the protocol will also be analyzed at this time.

- 1) To evaluate LPV characteristics (area under the curve [AUC], maximum concentration [ $C_{max}$ ], minimum concentration [ $C_{min}$ ]) in participants enrolled in Arms A, B, and C, accrual periods 1 and 2.
- 2) To evaluate the RBT PK characteristics (AUC,  $C_{max}$ ,  $C_{min}$ ) in participants enrolled in Arms A and C, accrual periods 1 and 2.
- 3) To evaluate RAL PK characteristics (AUC,  $C_{max}$ ,  $C_{min}$ ) in participants enrolled in Arm C, accrual period 2.

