Because the primary objective entails comparing virologic efficacy of Arm A versus Arm B and Arm C versus Arm A, we will have two hypothesis tests and will use an alpha-level of 0.025 for each test (thus, overall alpha-level = 0.05). If we assume the overall virologic efficacy of the double-dose LPV/r arm is 50%, and the standard LPV/r dosed arm coupled with RBT is 70% by 48 weeks (and 80-90% for LPV/r and RAL with RBT-based anti-TB treatment), 147 participants per arm will provide 90% power to detect a 20% difference in virologic response rates by 48 weeks between the double-dose LPV/r arm and the standard LPV/r plus RBT arm and adequate power for the comparison of the standard LPV/r plus RBT arm and adequate power for the comparison of the standard LPV/r plus RBT plus RAL arm compared to both other treatment arms. This assumes using a two-sample, two-sided 0.025-level asymptotically-normal binomial test.

Participants lost to follow-up will be considered as failures. Participants determined to have RIF-resistant TB isolates after enrollment will be taken off study, referred to their local clinician or clinical facility to receive best available local standard of care, and will not be replaced. Assuming that 3% of participants will have RIF resistance at entry and be taken off study, we will need to adjust the sample size to require 152 participants per arm. Adjusting the sample size again by 3% for interim analyses requires 157 participants per arm. Based on these data and assumptions, the estimated overall sample size will be 471 participants.

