#### 9.6.2 Analysis of the Primary Objective

All participants enrolled into A5290 will be included in the analysis of all the overall study objectives regardless of any required dose adjustments for accrual period 1 participants. The protocol team discussed the effect of including participants enrolled during accrual period 1 who underwent dose adjustments in the final analysis of the primary endpoint. The protocol team acknowledges that it is possible that those enrolled during accrual period 1 who had low LPV concentrations and required a dose adjustment might have worse HIV viral load responses at week 48, or alternatively, those who underwent a dose adjustment of one or more study-provided drugs might have greater toxicity that could adversely affect adherence, early treatment discontinuation, and HIV viral load responses at week 48. There remains significant uncertainty around what the major drivers will be of the week 48 virologic outcomes in this setting, such that including all participants in an intent-to-treat analysis accounting for all factors that might have contributed to the endpoint, including low levels requiring dose adjustment, higher toxicity leading to non-adherence or dose interruptions, prolonged intensive TB treatment phase, etc. will be a part of the study analysis plan. The protocol team also acknowledges that it is possible that those enrolled during the accrual period 1 could be different than those enrolled during the accrual period 2. Besides seeking as homogeneous a population as possible, baseline tables of factors that could affect drug concentrations (e.g., sex, prior ART experience, body weight, etc.) will be summarized by accrual period.

The primary outcome variable will be the rates of virologic suppression at 48 weeks within each treatment arm. Participants lost-to-follow-up or without virologic data will be considered failures (i.e., not suppressed). The rate in the double-dose LPV/r arm will be separately compared to the standard dose LPV/r arms in two analyses. The rates between the two arms will be compared using an asymptotic normal binomial test (Arm A versus Arm B; Arm C versus Arm B).

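### SAP 1.3 still plans 471 participants and an open accrual period 2, while SAP 1.6 says period 2 will not open; the sample size, the protocol's 90% power and the RAL objective's population need restating

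*SAP*

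**What the plan says.** SAP 1.3 (Protocol Overview) describes a trial that continues to full size. It states "471 participants will be randomized in a 1:1:1 ratio to receive either" one of the three regimens. On the first stage it says "Accrual period 1 will enroll 60 participants (20/arm) who will undergo an initial dose-finding period", and on the second "Accrual period 2 will open and randomize the remaining participants to either three arms (n=411) or to the remaining two arms (n=TBD"), with the DSMB to monitor it. The same section carries the primary hypothesis that standard-dose LPV/r "coupled with RBT-based TB treatment is superior to a double dose LPV/r regimen coupled with RIF-based TB treatment".

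SAP 1.6 (PK Study Objectives) says the opposite: "Since Accrual Period 2 will not open to enroll participants, the PK objectives outlined in the protocol will also be analyzed at this time". It then lists the objectives with the protocol's populations unchanged. LPV and rifabutin (RBT) are assigned to both accrual periods, and RAL is to be evaluated "in participants enrolled in Arm C, accrual period 2". SAP 5.2.3 plans RAL summaries in Arm C, names no accrual period, and labels a figure and a comparison table as serving that objective.

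Protocol 9.4.2 states that "147 participants per arm will provide 90% power to detect a 20% difference in virologic response rates by 48 weeks" and inflates this to 157 per arm, 471 in all. Protocol 9.6.2 prescribes the week-48 analysis in all enrolled participants: "The rates between the two arms will be compared using an asymptotic normal binomial test" (A v B and C v B).

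**The concern.** Both statements about period 2 are current text in one SAP dated 7 October 2016, and they cannot both be true. Section 1.6 reads as a decision already taken. Section 1.3 reads as protocol background that was not brought up to date.

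Two things are at stake. First, no document gives a revised sample size, qualifies the 90% power or says what becomes of the week-48 comparison. Someone who later sees that comparison beside the protocol's power statement could take a non-significant result as evidence that the regimens perform alike. Second, the RAL outputs are traced to an objective whose named population will not exist, so the SAP text available here does not say which participants and samples supply them.

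**Working it through.** **Inputs.** From protocol 9.4.2: 50% suppression in Arm B, 70% in Arm A, 80-90% in Arm C; two-sided 0.025 per comparison; normal-approximation test of two proportions; 90% power. From SAP 1.3: 20 per arm planned in period 1. Critical value z(0.9875) = 2.2414; z(0.90) = 1.2816.

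**Step 1: reproduce the planned size.** With pooled variance under the null and mean proportion 0.60:

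n = [2.2414 × √(2 × 0.60 × 0.40) + 1.2816 × √(0.25 + 0.21)]² / 0.20² = [2.2414 × 0.6928 + 1.2816 × 0.6782]² / 0.04 = 146.7, so 147 per arm.

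147/0.97 = 151.5, so 152 (rifampin resistance); 152/0.97 = 156.7, so 157 (interim analyses); 3 × 157 = 471; 471 − 60 = 411. The protocol's figures reproduce exactly. They were calculated correctly and depend on period 2.

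**Step 2: size without period 2.** Planned maximum 3 × 20 = 60, which is 60/471 = 12.7% of the planned total.

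**Step 3: power at that size.** Power = Φ[(d − 2.2414 × s0)/s1], where d is the difference, s0 = √(2p̄(1 − p̄)/n) and s1 = √((p1(1 − p1) + p2(1 − p2))/n).

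For 50% v 70% at n = 20: s0 = 0.1549, s1 = 0.1517, so (0.20 − 0.3472)/0.1517 = −0.971 and power = 0.166. At n = 147 the same formula gives Φ(1.286) = 0.901.

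| Arm B v comparator | n = 20, formula | n = 20, exact enumeration of the z test | n = 18, formula |
|---|---|---|---|
| 50% v 70% | 0.166 | 0.163 | 0.150 |
| 50% v 80% | 0.395 | 0.409 | 0.354 |
| 50% v 90% | 0.718 | 0.742 | 0.662 |

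With 20 per arm and 50% in Arm B, 90% power would need about 97% suppression in the comparator.

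**Step 4: precision.** Half-width at 50% v 70% = z × √(0.25/20 + 0.21/20) = z × 0.1517. This is 0.340 for a 97.5% interval (z = 2.2414) and 0.297 for a 95% interval (z = 1.96).

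**Step 5: the PK objectives set against SAP 1.6.** Objectives 1 and 2 cover both periods, so they keep their period 1 participants. Objective 3 covers period 2 only, so its named population is empty. In the protocol, RAL PK is a period 2 objective (1.3.12, 10.1.3). The period 1 sampling and quantitation sections (10.2.2, 10.2.4) specify RBT and LPV, with RAL mentioned only for dose timing. RAL quantitation is specified for period 2 (10.5.4).

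**The case against.** The strongest reply is that this is stale background. SAP 1.3 is headed as a protocol overview and feeds no table. SAP 1.1 limits the plan to the PK and safety interim report, and sections 2 to 6 contain no week-48 comparison and no power statement. The protocol itself allows enrolment to stop after period 1. All of this stands, and it rules out some stronger readings:

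- A reader might infer that the SAP is at fault for lacking an efficacy analysis. Given its scope, it is not.
- A reader might infer that the superiority hypothesis is now wrong. A smaller sample does not falsify a hypothesis; it removes the ability to test it at the planned power.
- A reader might infer that the test in protocol 9.6.2 must be replaced at 20 per arm. Its exact two-sided size there is at most about 0.0253 against the nominal 0.025, so its validity is not in question.
- A reader might infer that the RAL objective cannot be answered. SAP 5.2.3 already applies RAL to Arm C without naming a period, and if period 2 does not open those participants can only come from period 1. The fault is a population phrase left unchanged.
- A reader might assume that the RAL data are the day-12 intensive profiles. No available section says so, and part of the opening of SAP section 5 was not available, so sample details may be given there.

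The reply does not remove the conflict between 1.3 and 1.6. Nor does it supply a revised size, or a statement of what the 90% power now means for an analysis that protocol 9.6.2 still prescribes.

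**Conclusion.** The point holds as an internal contradiction with a material consequence. If SAP 1.6 is the current decision, 471 is no longer the trial's size and 90% power no longer describes the week-48 comparison. At the planned 20 per arm, A v B power is about 17%. C v B power is about 40% if Arm C reaches 80%, and 72-74% if it reaches 90%. A 97.5% interval at 50% v 70% spans about ±34 points, so a true 20-point advantage would usually go undetected.

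These figures assume the protocol's suppression rates and the planned period 1 enrolment. Actual enrolment is not given, and protocol 9.4.1 and 9.5.1 allowed extra period 1 participants; with 18 per arm, A v B power would be 15%. The decision not to open period 2 is not criticised here.

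**What to change.** - **SAP 1.3:** keep 471 only as the planned size, record that accrual stopped after period 1, and give the actual number randomised per arm. Remove or qualify the sentence saying that period 2 will open.
- **SAP 1.6:** limit objectives 1 and 2 to accrual period 1. Reword objective 3 to Arm C, accrual period 1, and name the samples that supply the RAL analysis, so that the tables in 5.2.3 trace to a population that exists.
- **Protocol 9.4.2 and 9.6.2, or the plan that covers week 48:** add a note that the 90% power no longer applies, that the A − B and C − B differences in suppression will be reported with confidence intervals, and that a non-significant result will not be read as evidence of no difference. The prescribed test can stay.

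The cost is minor wording in the SAP, a short note to the protocol and a less favourable stated power. No new data or participants are needed.
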